10.2.3 Data Monitoring Committee

There is no Data Monitoring Committee (DMC) for this trial.

10.2.4 Infection surveillance

All infections that develop during the study will be reported as AEs. Investigators are requested to specifically enquire about signs and symptoms of infections at each visit, in particular for encapsulated bacteria. Beta-lactam, macrolide and quinolone antibiotics can be used for prophylactic treatment in accordance with local practice. A suggested regimen would include Ciprofloxacin 500 mg p.o. b.i.d. x 14 days followed by long term treatment with Penicillin V 500 mg p.o. b.i.d. or erythromycin 500 mg p.o b.i.d. for patients intolerant to penicillin V while on LNP023. Choice and regimen of antibiotic treatments needs to be adjusted to local requirements and guidelines. Other additional evaluations will be performed at the discretion of the investigator.

11 Data Collection and Database management

11.1 Data collection

Designated investigator staff will enter the data required by the protocol into the Electronic Case Report Forms (eCRF). The eCRFs have been built using fully validated secure web-enabled software that conforms to 21 CFR Part 11 requirements, investigator site staff will not be given access to the EDC system until they have been trained. Automatic validation programs check for data discrepancies in the eCRFs, allow modification and/or verification of the entered data by the investigator staff.

The investigator/designee is responsible for assuring that the data (recorded on CRFs) (entered into eCRF) is complete, accurate, and that entry and updates are performed in a timely manner. The investigator must certify that the data entered are complete and accurate. Certain data may be captured via other source documentation (such as safety laboratory data report) and then transcribed, uploaded or transferred into the system. This, and any additional data treated in this manner, will be source data verified by the study monitor per the monitoring plan and the location of source data (i.e., source, paper or a local electronic system) will be documented prior to study start in the Data Quality Plan. The system has the ability to illustrate when a document has been entered from another source. When using an electronic source record as the original point of data capture, there is no additional data entry step for the site for data collected directly into the application; rather, the electronic source record directly populates the study database. Automatic validation programs check for data discrepancies and, by generating appropriate error messages, allow the data to be confirmed or corrected before transfer of the data to sponsor. Remote monitoring of the original electronic source records will take place, however on-site monitoring inspections will continue to take place in order to review data entry of source documentation directly captured on paper and transcribed into the system, to ensure protocol adherence, to assess site operational capabilities, and to perform other monitoring activities that cannot be performed remotely.

After final database lock, the investigator will receive copies of the subject data for archiving at the investigational site.

All data should be recorded, handled, and stored in a way that allows its accurate reporting, interpretation, and verification.

11.2 Database management and quality control

Novartis personnel (or designated CRO) will review the data entered by investigational staff for completeness and accuracy. Electronic data queries stating the nature of the problem and requesting clarification will be created for discrepancies and missing values and sent to the investigational site via the EDC system. Designated investigator site staff are required to respond promptly to queries and to make any necessary changes to the data.

Concomitant treatments and prior medications entered into the database will be coded using the World Health Organization (WHO) Drug Reference List, which employs the Anatomical Therapeutic Chemical classification system. Medical history/current medical conditions and adverse events will be coded using the Medical Dictionary for Regulatory Activities (MedDRA) terminology.

Randomization codes and data about all study treatment (s) dispensed to the subject and all dosage changes will be tracked using an Interactive Response Technology (IRT). The system will be supplied by a vendor, who will also manage the database. The data will be sent electronically to Novartis at specific timelines.

Each occurrence of a code break via IRT for LNP023 regimens will be reported to the clinical team and monitor. The code break functionality will remain available until study shut down or upon request of Novartis.

Once all the necessary actions have been completed and the database has been declared to be complete and accurate, it will be locked **and the treatment codes will be unblinded** and made available for data analysis. Any changes to the database after that time can only be made after written agreement by Novartis development management.

11.3 Site monitoring

Before study initiation, at a site initiation visit or at an investigator's meeting, a Novartis or delegated CRO representative will review the protocol and data capture requirements (i.e. eCRFs) with the investigators and their staff. During the study, Novartis employs several methods of ensuring protocol and GCP compliance and the quality/integrity of the sites' data. The field monitor will visit the site to check the completeness of subject records, the accuracy of data capture / data entry, the adherence to the protocol and to Good Clinical Practice, the progress of enrollment, and to ensure that study treatment is being stored, dispensed, and accounted for according to specifications. Key study personnel must be available to assist the field monitor during these visits. Continuous remote monitoring of each site's data may be performed by a centralized Novartis/delegated CRO/CRA organization. Additionally, a central analytics organization may analyze data & identify risks & trends for site operational parameters, and provide reports to Novartis clinical teams to assist with trial oversight.

The investigator must maintain source documents for each subject in the study, consisting of case and visit notes (hospital or clinic medical records) containing demographic and medical information, laboratory data, electrocardiograms, and the results of any other tests or assessments. All information on CRFs must be traceable to these source documents in the subject's file. The investigator must also keep the original informed consent form signed by the subject (a signed copy is given to the subject).

The investigator must give the monitor access to all relevant source documents to confirm their consistency with the data capture and/or data entry. Novartis monitoring standards require full verification for the presence of informed consent, adherence to the inclusion/exclusion criteria, documentation of SAEs, and of data that will be used for all primary variables. Additional checks of the consistency of the source data with the CRFs are performed according to the study-specific monitoring plan. No information in source documents about the identity of the subjects will be disclosed.

12 Data analysis and statistical methods

The analysis will be conducted on all subject data at the time when an interim analysis occurs or when the trial ends.

Any data analysis carried out independently by the investigator should be submitted to Novartis before publication or presentation.

Commercially Confidential Information

12.1 Analysis sets

For all analysis sets, subjects will be analyzed according to the study treatment(s) received.

The full analysis set (FAS) will include all randomized subjects.

The safety analysis set will include all subjects that received any study drug.

The PK analysis set will include all subjects with at least one available valid (i.e. not flagged for exclusion) PK concentration measurement, who received any study drug and with no protocol deviations that impact on PK data.

The PD analysis set will include all subjects that receive any study treatment and no protocol deviations with relevant impact on PD/efficacy data.

12.2 Subject demographics and other baseline characteristics

Demographic and other baseline data including UPCR, PLA2R CCI will be summarized descriptively by treatment group for the FAS.

Categorical data will be presented as frequencies and percentages. For continuous data, mean, standard deviation, median, minimum, and maximum will be presented.

Relevant medical histories and current medical conditions at baseline will be summarized separately by system organ class and preferred term, by treatment group.

12.3 Treatments

The Safety set will be used for the analyses below. Categorical data will be summarized as frequencies and percentages. For continuous data, mean, standard deviation, median, minimum, and maximum will be presented.

The duration of exposure in weeks to study treatment will be summarized by means of descriptive statistics using the safety set. Concomitant medications and significant non-drug therapies prior to and after the start of the study treatment will be listed and summarized according to the Anatomical Therapeutic Chemical (ATC) classification system, by treatment group.

12.4 Analysis of the primary endpoint(s)

The primary aim of the study is to assess the reduction in UPCR (measured in 24h urine) in LNP023 200 mg treated subjects compared with rituximab after 24 weeks of treatment.

In the LNP023 treatment groups patients are considered as under treatment whilst taking the treatment and 30 days after the last administration. In the Rituximab arm, patients are considered as under treatment if they received both injections, or 3 months after they received the single injection.

12.4.1 Definition of primary endpoint(s)

The primary endpoint of this study is the ratio between baseline UPCR and UPCR at 24 weeks of treatment measured in 24h urine. This endpoint will be log-normal transformed prior to analysis, as it is assumed to follow a log-normal distribution.

12.4.2 Statistical model, hypothesis, and method of analysis

To assess the primary objective, UPCR will be analyzed using a mixed model for repeated measures. The results will be back transformed and presented on the original scale.

Commercially Confidential Information

The following two criteria will be used to assess treatment efficacy:

- Statistically significant decrease (no worse than 55% increase) in UPCR at week 24 visit in LNP023 200 mg -treated subjects vs. rituximab-treated subjects at one-sided 10% level (i.e. $H_0 : (\text{ratio from BL in UPCR_LNP}) / (\text{ratio from BL in UPCR_Ritux}) \geq 1.55$)
- Estimated mean reduction in UPCR in LNP023 200 mg-treated subjects better than 10% increase vs rituximab-treated subjects (i.e. $(\text{ratio from BL in UPCR_LNP}) / (\text{ratio from BL in UPCR_Ritux}) < 1.1$)

12.4.3 Handling of missing values/censoring/discontinuations

All subjects with at least one post baseline measurement of UPCR in 24h urine will be used in the analysis. The primary Mixed effect Model Repeat Measurement (MMRM) model implicitly imputes missing data under a missing at random assumption.

12.4.4 Supportive analyses

Commercially Confidential Information

12.5 Analysis of secondary endpoints

Details of the statistical methodologies for the secondary endpoints will be described in the SAP. Graphical presentation of the data will be performed where applicable.

12.5.2 Safety endpoints

For all safety analyses, the safety set will be used. All tables will be presented by treatment group.

Safety summaries (tables, figures) include only data from the on-treatment period with the exception of baseline data which will also be summarized where appropriate (e.g. change from baseline summaries). In particular, summary tables for adverse events (AEs) will summarize only on-treatment events, with a start date during the on-treatment period (treatment-emergent AEs).

The on-treatment period in the LNP023 treatment groups lasts from the date of first administration of study treatment to 30 days after the date of the last actual administration of any study treatment. The on-treatment period in the rituximab treatment group lasts from the first administration to 6 months after the date of the second administration. Subjects who received a single rituximab infusion are considered under treatment until 3 months after this single infusion.

Adverse events

All information obtained on adverse events will be displayed by treatment group and subject.

The number (and percentage) of subjects with treatment emergent adverse events (events started after the first dose of study medication or events present prior to start of treatment but increased in severity based on preferred term) will be summarized in the following ways:

- by treatment, primary system organ class and preferred term;
- by treatment, primary system organ class, preferred term and maximum severity;
- by treatment, Standardized MedDRA Query (SMQ) and preferred term.

Separate summaries will be provided for study medication related adverse events, death, serious adverse events, other significant adverse events leading to discontinuation.

The number (and proportion) of subjects with adverse events of special related to identified and potential risks (i.e. systemic bacterial infection, anaemia, abnormalities of thyroid function and testicular symptoms and / or abnormalities of reproductive hormone levels) will be summarized by treatment.

A subject with multiple adverse events within a primary system organ class is only counted once towards the total of the primary system organ class.

Adverse events which will be counted for a specific treatment period are those which are treatment-emergent. These events are those with an onset after the start of the treatment period, or which were present prior to the start of the treatment period but increased in severity, changed from being not suspected to being suspected of study drug relationship, or developed into SAEs after the start of the treatment period.

Heatmaps will be provided by treatment group displaying the on- and off-set of the most severe AE in a subject over time.

Vital signs

Summary statistics will be provided on all vital signs data by treatment and visit/time.

12-lead ECG

PR, QRS, QT, QTcF, and RR intervals will be obtained from 12-lead ECGs for each subject during the study. ECG data will be read and interpreted (locally). Summary statistics will be provided on all ECG data by treatment and visit/time.

Clinical laboratory evaluations

Summary statistics will be provided on all laboratory data by treatment and visit/time. Shift tables using the low/normal/high/ (low and high) classification will be used to compare baseline to the worst on-treatment value.

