Given the absence of a well-tolerated efficacious therapy for this disorder, there is a strong case for investigating the potential efficacy of LNP023 as an agent to reduce glomerular injury, through inhibition of the complement alternative pathway. Our hypothesis is that complement inhibition will reduce ongoing glomerular inflammation and resultant glomerulosclerosis, reducing the rate of deterioration in kidney function.

Comprehensive information is available in the Investigator Brochure.

2 Objectives and endpoints

Table 2-1 Objectives and related endpoints

Objective(s)	Endpoint(s)
Primary objective(s)	Endpoint(s) for primary objective(s)

To assess the efficacy of LNP023 compared with rituximab	
Ratio between baseline UPCR and UPCR at 24 weeks of treatment (from 24h urine collection)
Secondary objective(s)	Endpoint(s) for secondary objective(s)

To assess the safety and tolerability of LNP023To assess the effect of LNP023 compared with rituximab on proteinuria remission and renal functionTo assess the pharmacokinetics of LNP023	
ECG parameters, vital signs, safety laboratory data, physical exam and collection of AEs assessed from baseline until the end of the study visit.Plasma levels of Bb and sC5b-9UPCR measured in first morning voidNon-compartmental parameters related to drug exposureProportion of subjects with a complete remission, defined as proteinuria ≤ 0.3 g/day at 24 weeks of treatment, derived from 24h urine collectionProportion of subjects with a partial remission, defined as reduction of proteinuria from baseline $\geq 50\%$ plus final UP ≤ 3.5 g/24h but >0.3 g/24h at 24 weeks of treatment, derived from 24h urine collection.Change in eGFR applying the Chronic Kidney Disease Epidemiology Collaboration (CKD-EPI) equation from baseline to 24 weeks of treatmentPlasma: non-compartmental parameters in plasma related to total parent drug, including, but not limited, to Tmax, Cmax, AUClast and AUCtau will be calculated for each dose level.Urine: renal plasma clearance derived from 24h urine at week 16.

Commercially Confidential Information

Objective(s)	Endpoint(s)
Exploratory objective(s)	Endpoint(s) for exploratory objective(s)
Commercially Confidential Information	

3 Study design

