At baseline, laboratory tests, collection of first morning void urine and 24h urine will be performed. To minimize the number of subjects likely to undergo spontaneous disease remission from entering the study and potentially biasing the results through over-representation in any of the study arms, those subjects in whom the 24h urine protein level or anti-PLA2R antibody titer fall by more than 50% compared to first measurement at screening or run-in visit, and those in whom the 24h urine protein level has fallen below 3.5g/24h will be considered a baseline failure and will not proceed to receive any study drug. Baseline period can be extended in case of delays in receiving the anti-PLA2R results.

Subjects are randomized on Day 1 or up to 4 days before, only after eligibility is confirmed, to LNP023 or rituximab.

Treatment period (subjects randomized to the LNP023 treatment arm)

Treatment period lasts for 24 weeks from Day 1 to Day 169:
Commercially Confidential Information

Treatment period (subjects randomized to the rituximab treatment arm)

- Day 1 and Day 15: a dose of rituximab 1 g by intravenous infusion (i.v.), will be administered (refer to [Section 6.1.1](#) for more details).
- Subjects should receive pre-medication consisting of an anti-pyretic and an antihistamine (e.g. paracetamol and diphenhydramine) before each dose as per local standards. Where a single dose of glucocorticoid (e.g. methylprednisolone or hydrocortisone) is used in addition to these measures as part of local standard of care, then this is permitted.
- Treatment period will continue till Day 169 without any further rituximab administration.

Safety follow-up and EOS

A safety follow-up period of 29 weeks will follow the treatment period. A call should be performed 30 days after the last day of the treatment period (Day 199, week 28), and a study visit will be performed on Day 266 (Week 37). Subjects may be treated according to local standard of care throughout this follow-up period. All treatments administered should be documented in the study Case Report Forms.

An EOS visit is scheduled on Day 378 (week 53).

Please refer to [Section 8](#) for details regarding assessments to be performed.

4 Rationale

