9.1 Discontinuation

9.1.1 Discontinuation of study treatment

Discontinuation of study treatments for a patient occurs when study treatment is stopped earlier than the protocol planned duration. Discontinuation of study treatment can be decided by either the patient or the investigator. If discontinuation of study treatment occurs, the investigator must determine the primary reason for the patient's premature discontinuation of study treatment and record this information on the Dosage Administration CRF.

Patients who discontinue study treatment or who decide they do not wish to participate in the study further should NOT be considered withdrawn from the study UNLESS they withdraw their consent. Where possible, they should perform the assessments as per assessment schedule. If they fail to return for these assessments for unknown reasons, every effort (e.g. telephone, e-mail, letter) should be made to contact the patient/pre-designated contact as specified. This contact should preferably be done according to the study visit schedule.

Test treatment (LNP023) or reference treatment (rituximab) must be discontinued under the following circumstances:

- Patient decision - Patients may choose to discontinue study treatment for any reason at any time.
- The investigator believes that continuation would negatively impact the safety of the patient or the risk/benefit ratio of trial participation.
- Any protocol deviation that results in a significant risk to the patient's safety.
- Pregnancy
- Infections that are considered, by the investigator, not possible to effectively manage whilst the patient is receiving LNP023 or rituximab.
- Use of prohibited treatment as outlined in [Table 6-2](#) and [Table 6-3](#) listing prohibited medications
- Any laboratory abnormalities that in the judgment of the investigator, taking into consideration the patient's overall status, prevents the patient from continuing participation in the study.
- Please see [Section 16.1 Appendix 1](#) for additional information on discontinuing treatment based on laboratory evidence of liver injury.

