- Drug interrupted/withdrawn

6. its outcome: not recovered/not resolved; recovered/resolved; recovered/resolved with sequelae; fatal; or unknown

Conditions that were already present at the time of informed consent should be recorded in medical history of the subject.

Adverse events (including lab abnormalities that constitute AEs) should be described using a diagnosis whenever possible, rather than individual underlying signs and symptoms.

Adverse event monitoring should be continued for at least 30 days (or 5 half-lives or end of study visit, whichever is longer) following the last dose of study treatment.

Information about adverse drug reactions for the investigational drug can be found in the IB.

Abnormal laboratory values or test results constitute adverse events only if they fulfill at least one of the following criteria:

- they induce clinical signs or symptoms
- they are considered clinically significant
- they require therapy

Clinically significant abnormal laboratory values or test results must be identified through a review of values outside of normal ranges/clinically notable ranges, significant changes from baseline or the previous visit, or values which are considered to be non-typical in subjects with the underlying disease.

Follow the instructions found in the Site Operations Manual for data capture methodology regarding AE collection for subjects that fail screening.

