### 1.3 Study objectives

Objective(s)	Endpoint(s)
Primary objective(s)	Endpoint(s) for primary objective(s)

• To assess the efficacy of LNP023 compared with rituximab

	

• Ratio between baseline UPCR and UPCR at 24 weeks of treatment (from 24h urine collection)

Secondary objective(s)	Endpoint(s) for secondary objective(s)

• To assess the safety and tolerability of LNP023

	

• ECG parameters, vital signs, safety laboratory data, physical exam and collection of AEs assessed from baseline until the end of the study visit.

Commercially Confidential Information	

• Plasma levels of Bb and sC5b-9

• UPCR measured in first morning void

• Non-compartmental PK parameters related to drug exposure

• To assess the effect of LNP023 compared with rituximab on proteinuria remission and renal function

	

• Proportion of subjects with a complete remission, defined as proteinuria <math>\leq 0.3</math> g/day at 24 weeks of treatment, derived from 24h urine collection

• Proportion of subjects with a partial remission, defined as reduction of proteinuria from baseline <math>\geq 50\%</math> plus final UP <math>\leq 3.5</math> g/24h but <math>> 0.3</math> g/24h at 24 weeks of treatment, derived from 24h urine collection.

• Change in eGFR applying the Chronic Kidney Disease Epidemiology Collaboration (CKD-EPI) equation from baseline to 24 weeks of treatment

Objective(s)	Endpoint(s)

• To assess the pharmacokinetics of LNP023

	

• Plasma: non-compartmental PK parameters in plasma related to total parent drug, including, but not limited, to Tmax, Cmax, AUClast and AUCltau will be calculated for each dose level.

• Urine: renal plasma clearance derived from 24h urine at week 16.

Exploratory objective(s)	Endpoint(s) for exploratory objective(s)

Commercially Confidential Information

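### The safety endpoint runs to Day 378 but the safety tables stop near Day 199, so later deaths, SAEs and AESIs are listed but not counted by arm

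*Protocol*

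**What the plan says.** **Endpoint.** Protocol Table 2-1 lists, for the secondary safety objective, ECG, vital signs, laboratory data, "physical exam and collection of AEs assessed from baseline until the end of the study visit". SAP 1.3 has the same window: "collection of AEs assessed from baseline until the end of the study visit". Protocol section 3 schedules the end-of-study visit on Day 378.

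**Follow-up and collection.** Protocol section 3 states: "A safety follow-up period of 29 weeks will follow the treatment period". Protocol 10.1.1 continues adverse event monitoring to the longest of three limits, one of which is the end-of-study visit. Tables 8-1 and 8-2 schedule vital signs, haematology and chemistry at Day 266 and Day 378 in both arms. For subjects who stop treatment early, Protocol 9.1.1 adds: "Where possible, they should perform the assessments as per assessment schedule".

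**Summary rule.** Protocol 12.5.2 states: "Safety summaries (tables, figures) include only data from the on-treatment period", except for baseline values. It adds that adverse event tables count only events that begin within that period. SAP section 7 repeats the general rule. Both documents define the period alike:
- LNP023: first dose to 30 days past the last dose.
- Rituximab, two infusions: first infusion to 6 months past the second.
- Rituximab, one infusion: to 3 months past that infusion.

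**Outputs without a window.** Protocol 12.5.2 and SAP 7.2 display all adverse event information by treatment and subject, and SAP 7.2 does the same for AESIs. These are listings.

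**The concern.** The declared window of the endpoint and the window of its tables differ by roughly half a year for a completer. The plan collects adverse events throughout a period that it calls safety follow-up, then excludes that period from every table and figure by an explicit rule.

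At stake is the reporting of the events that matter most. Followed as written, the plan produces no by-arm number of deaths, SAEs or AESIs that begin after the on-treatment period, and a reader would have to count them from listings. Subjects who stop treatment early leave the tables soonest, although they are asked to stay in assessment where possible. The primary efficacy analysis is not affected.

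**Working it through.** The check is day arithmetic on nominal visit days.

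**Inputs**
- End of treatment period: Day 169. End-of-study visit: Day 378 (Protocol section 3).
- Rituximab infusions: Day 1 and Day 15 (Protocol section 3).
- On-treatment rules: Protocol 12.5.2 and SAP section 7.
- Assumptions: last LNP023 dose on Day 168 or 169; 6 calendar months = 181-184 days; 3 calendar months = 89-92 days.

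**Reproducing the plan's own figure.** Protocol section 3 puts the call 30 days after the end of treatment on Day 199. 169 + 30 = 199, which agrees.

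**End of the on-treatment period**
- LNP023 completer: 168 + 30 to 169 + 30 = Day 198-199.
- Rituximab, two infusions: 15 + 181 to 15 + 184 = Day 196-199.
- Rituximab, one infusion: 1 + 89 to 1 + 92 = Day 90-93.
- LNP023 stopped early with last dose on Day d: Day d + 30.

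**Time outside the tables = 378 minus the end day**
- Completers: 378 - 199 = 179 days (179/378 = 47.4%) to 378 - 196 = 182 days (182/378 = 48.1%). The Day 266 and Day 378 visits both fall here.
- As a share of follow-up after Day 169: 378 - 169 = 209 days; 179/209 = 85.6% to 182/209 = 87.1%.
- One rituximab infusion, subject still followed: 378 - 93 = 285 days (75.4%) to 378 - 90 = 288 days (76.2%).
- LNP023 stopped early, subject still followed: 378 - (d + 30) = 348 - d days. For illustration, d = 85 gives 263 days (263/378 = 69.6%).

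**Sensitivity**
- Counting 6 months as 180 days: 15 + 180 = Day 195, leaving 183 days (48.4%).
- Visit windows: last LNP023 dose Day 166-172 gives Day 196-202; second infusion Day 13-17 gives Day 194-201. The time outside is then 378 - 202 = 176 days (46.6%) to 378 - 194 = 184 days (48.7%).

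**Is there a count elsewhere?** The separate summaries of deaths, SAEs and AESIs in Protocol 12.5.2 and SAP 7.2 come under the on-treatment rule. The SAP 7.2 sentence on numbers of deaths names no window, and the SAP definition of a treatment-emergent event gives a start but no end. Both sit inside section 7, so its general rule governs them, and Protocol 12.5.2 supplies the end date. The visible text contains no post-treatment or whole-study table.

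**The case against.** **The window is prespecified and reasonable.** The endpoint wording can be read as the period of assessment, with the tabulation window then set openly and identically in both documents. On-treatment tables are a sound choice for attribution to drug. This stands: a reader might infer that the two passages contradict each other, but the documents support only a gap between what is collected and what is counted.

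**Nothing is lost.** Later events are collected and listed by treatment and subject. With approximately 24 subjects per arm, the listing should be short enough to count by hand. This also stands and limits the consequence, but a listing is not a planned count.

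**Follow-up is confounded.** Protocol section 3 states: "Subjects may be treated according to local standard of care throughout this follow-up period". The secondary safety objective concerns LNP023 itself, and the study is a non-confirmatory proof of concept. So later counts cannot support attribution to an arm. That is a reason to show them separately with a label; it does not justify having no count.

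**The SAP may already count later deaths.** Read alone, the death sentence in SAP 7.2 could admit them. Under the section 7 rule the likelier reading is that it does not.

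**A stronger claim about SAEs is tempting.** A reader might infer that SAEs are always collected to 30 days after the end-of-study visit, about Day 408 (378 + 30), and that SAE counts for early stoppers fall short accordingly. Protocol 10.1.3 does not settle this. Its opening paragraph ends reporting 30 days after the last study visit. Its paragraph on randomized subjects ends collection 30 days after stopping study treatment or completing the last visit. On the first alternative, collection for an early LNP023 stopper could end about when the on-treatment period ends. No SAE shortfall should be computed until the two statements are reconciled.

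**Conclusion.** The point holds as a reporting gap created by an explicit rule. For completers, about 179-182 of 378 days (47-48%) of the declared endpoint window lie outside all safety tables and figures. In the visible text, deaths, SAEs and AESIs that begin after the on-treatment period have no by-arm count.

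This rests on nominal visit days and calendar months; protocol visit windows move the share only to 46.6-48.7%. The 75-76% figure applies only to a rituximab subject with a single infusion who stays in follow-up, and the documents do not say how many to expect.

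Two further inferences are not supported. The percentages measure calendar time and say nothing about the share of events. The cut-off is also similar in the two arms for completers, so no imbalance between arms follows. Parts of the SAP are blacked out, so the absence of a table is claimed for the visible text only, although section 7 is largely visible. The change is worth making because it is cheap; it is not a defect in the primary analysis.

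**What to change.** Keep the on-treatment tables as they are. In SAP section 7:
- Add descriptive by-arm tables of deaths, SAEs and AESIs with onset from first dose to end of study, with subject-time per arm.
- Show them separately from the on-treatment tables, with a label saying that they do not support attribution to an arm because standard-of-care treatment is allowed in follow-up.
- As a clarification only, state the window beside the death counts and the treatment-emergent definition.

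In Protocol 10.1.3, reconcile the two statements of when SAE collection ends, so that the last date covered by the new SAE table is known.

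This does not tabulate the whole endpoint. Non-serious events, and the laboratory and vital-sign results at Day 266 and Day 378, would stay outside the tables, which is an acceptable choice.

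The cost is one window flag, subject-time per arm, three tables and a short text edit, with no new data. The downside is that the follow-up counts are confounded by later treatment and could be over-read, hence the label.
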